6.4 Study Treatment Compliance

The prescribed dosage, timing and mode of administration may not be changed. Any departures from the intended regimen must be recorded in the eCRFs.

All study medications will be administered by the Investigator or designee. Subject noncompliance is therefore not applicable.

If a subject misses a dose, the dose should be administered as close as possible to the missed scheduled dose, but there should be at least 2 weeks between doses. If a period of 2 weeks between doses is not possible, then the missed scheduled dose should not be administered and the subject dosing should resume with the next scheduled dosing.

6.5 Concomitant Therapy

Any medication or vaccine (including over-the-counter or prescription medicines, vitamins and/or herbal supplements) that the subject is receiving at the time of enrolment (within 28 days before the time of enrolment) or receives during the study must be recorded on the eCRF along with:

- Reason for use
- Dates of administration including start and end dates
- Dosage information including dose and frequency

The Medical Monitor should be contacted if there are any questions regarding concomitant or prior therapy.

The use of stable doses of NSAIDs/COX-2 is permitted within 28 days prior to randomisation and during the study; the use of stable doses of MTX, sulfasalazine or leflunamide is permitted from 28 days prior to Screening and during the study.

The use of stable oral corticosteroids (≤ 10 mg) is permitted from 28 days prior to Baseline and during the study.

A list of excluded medications/therapy is provided in Appendix 5.

6.6 **Dose Modification**

No dose modifications are permitted in this study.

6.7 Treatment after the End of the Study

The Sponsor will not provide any additional care to subjects after they leave the study because such care should not differ from what is normally expected for subjects with axSpA.

7.0 DISCONTINUATION OF STUDY TREATMENT AND SUBJECT DISCONTINUATION/WITHDRAWAL

7.1 Discontinuation of Study Treatment

Subjects may be discontinued from study treatment for the following reasons:

- 1. Pre-treatment event or treatment-emergent AE. The subject has experienced a pre-treatment event or a treatment-emergent AE that requires early termination because continued participation imposes an unacceptable risk to the subject's health or the subject is unwilling to continue because of the pre-treatment event or AE.
 - Liver Function Test Abnormalities
 - Study medication must be discontinued immediately with appropriate clinical follow-up (including repeat laboratory tests) until the subject's laboratory profile has returned to normal/baseline status, if the following circumstances occur at any time during study medication treatment:
 - ALT or AST $> 8 \times$ ULN, or
 - ALT or AST $>5 \times$ ULN and persists for more than 2 weeks, or
 - ALT or AST >3 × ULN in conjunction with elevated total bilirubin >2 × ULN or international normalised ratio (INR) >1.5, without any anti-coagulant treatment, or
 - ALT or AST >3 × ULN with appearance of fatigue, nausea, vomiting, right upper quadrant pain or tenderness, fever, rash and/or eosinophilia (>5%).
- 2. If a diagnosis of PAP is confirmed during the course of this study (see Section 8.2.4), the subject should be withdrawn and treatment initiated as applicable.
- 3. Major protocol deviation. The discovery post-randomisation that the subject failed to meet protocol entry criteria or did not adhere to protocol requirements, and continued participation poses an unacceptable risk to the subject's health.
- 4. Lost to follow-up. The subject did not return to the clinic and attempts to contact the subject were unsuccessful. Attempts to contact the subject must be documented.
- 5. Pregnancy. The subject is found to be pregnant.

Subjects who discontinue study treatment will not be replaced.

See the SoA for data to be collected at the time of treatment discontinuation and follow-up and for any further evaluations that need to be completed.

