8.0 STUDY ASSESSMENTS AND PROCEDURES

Study procedures and their timing are summarised in the SoA.

Protocol waivers or exemptions are not allowed.

Clinically significant safety concerns should be discussed with the Sponsor immediately upon occurrence or awareness to determine if the subject should continue or discontinue study treatment.

Adherence to the study design requirements, including those specified in the SoA, is essential and required for study conduct.

All screening evaluations must be completed and reviewed to confirm that potential subjects meet all eligibility criteria. The Investigator will maintain a screening log to record details of all subjects screened and to confirm eligibility or record reasons for screening failure, as applicable.

Procedures conducted as part of the subject's routine clinical management (e.g., blood count) and obtained before signing of the ICF may be utilised for screening or baseline purposes provided the procedures met the protocol-specified criteria and were performed within the time frame defined in the SoA.

The maximum amount of blood collected from each subject over the duration of the study, including any extra assessments that may be required, will not exceed 250 mL. Repeat or unscheduled samples may be taken for safety reasons or for technical issues with the samples.

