8.2.8 Clinical Safety Laboratory Assessments

See Appendix 3 for the list of clinical laboratory tests to be performed and the SoA for the timing and frequency.

The Investigator must review the laboratory report, document this review and record any clinically relevant changes occurring during the study in the AE section of the CRF. The laboratory reports must be filed with the source documents. Clinically significant abnormal

laboratory findings are those that are not associated with the underlying disease, unless judged by the Investigator to be more severe than expected for the subject's condition.

All laboratory tests with values considered clinically significantly abnormal during participation in the study or within 18 weeks after the last dose of study treatment should be repeated until the values return to normal or baseline or are no longer considered clinically significant by the Investigator or Medical Monitor.

If such values do not return to normal/baseline within a period of time judged reasonable by the Investigator, the aetiology should be identified and the Sponsor notified.

All protocol-required laboratory assessments, as defined in Appendix 3, must be conducted in accordance with the laboratory manual and the SoA.

If laboratory values from non-protocol specified laboratory assessments performed at the institution's local laboratory require a change in subject management or are considered clinically significant by the Investigator (e.g., SAE or AE or dose modification), then the results must be recorded in the eCRF.

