Appendix 3 Clinical Laboratory Tests

The tests detailed in Table 13 will be performed by the local laboratory at each Investigator site.

Additional tests may be performed at any time during the study as determined necessary by the Investigator or required by local regulations.

Laboratory Assessments	Parameters					
	Platelet Count	RBC Indices: Mean corpuscular volume (MCV)		RBC Indices: White Blood Cell Count with		
	Red Blood Cell (RBC) Count			 L N	Differential : Neutrophils	
Haematology	Haemoglobin	Mean corpuscular hae (MCH)	emoglobin	L	Lymphocytes	
	Haematocrit	Mean corpuscular haemoglobin concentration (MCHC) %Reticulocytes		Ĭ	Monocytes Eosinophils Basophils	
Clinical Chemistry ^a	Blood Urea Nitrogen	Potassium	Aspartate Aminotransferase (AST)/Serum Glutamic- Oxaloacetic Transaminase (SGOT) Alanine Aminotransferase (ALT)/Serum Glutamic-Pyruvic Transaminase (SGPT)		Total and direct bilirubin	
	Creatinine	Sodium			Total Protein	
	Glucose	Calcium	Alkaline phosphatase		albumin	
		Chloride	Phosp	ohorous		
Serum Lipids	Total cholesterol	Triglycerides	HDL		LDL	
Biomarkers	Faecal calprotectin	C-reactive protein (CRP)	HLA-B27		Erythrocyte sedimentation rate	
	Stool sample for microbiome analysis					
Immunophenotyping						
Immunogenicity	Anti-namilumab antibodies					

Table 13Protocol Required Safety Laboratory Assessments

Laboratory Assessments	Parameters
Routine Urinalysis	 Specific gravity pH, glucose, protein, blood, ketones, bilirubin, urobilinogen, nitrite, leukocyte esterase by dipstick Microscopic examination (if blood or protein is abnormal)
Other Screening Tests	 Follicle-stimulating hormone and estradiol (as needed in women of non-childbearing potential only) Serum or urine human chorionic gonadotropin (hCG) pregnancy test (as needed for women of childbearing potential)^b Serology: Hepatitis B (hepatitis B virus surface antigen [HBsAg] positive [+] or detected sensitivity on the hepatitis B virus [HBV] DNA polymerase chain reaction [PCR] qualitative test for hepatitis B core antibodies [HBc Ab]/hepatitis B surface antibody [HBsAb] positive subjects) or hepatitis C (hepatitis C virus [HCV] RNA detectable in any subject with anti-hepatitis C virus antibody [HCV Ab]). ANA (anti-dsDNA titres if ANA is positive) QuantiFERON-TB test (or equivalent test)

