^a Details of liver chemistry stopping criteria and required actions and follow-up assessments after liver stopping or monitoring event are given in Section 7.1. All events of ALT ≥3 × upper limit of normal (ULN) and bilirubin ≥2 × ULN (>35% direct bilirubin) or ALT ≥3 × ULN and international normalised ratio (INR) >1.5, if INR measured, which may indicate severe liver injury (possible Hy's Law), must be reported as an SAE (excluding studies of hepatic impairment or cirrhosis).

^b Local urine testing will be standard for the protocol unless serum testing is required by local regulation or IRB/IEC.

Investigators must document their review of each laboratory safety report.

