Appendix 4Adverse Events: Definitions and Procedures for Recording,
Evaluating, Follow-up, and Reporting

Definition of AE

AE Definition

- An AE is any untoward medical occurrence in a patient or subject, temporally associated with the use of study treatment, whether or not considered related to the study treatment.
- NOTE: An AE can therefore be any unfavourable and unintended sign (including an abnormal laboratory finding), symptom, or disease (new or exacerbated) temporally associated with the use of study treatment.

Events Meeting the AE Definition

- Any abnormal laboratory test results (haematology, clinical chemistry, or urinalysis) or other safety assessments (e.g., ECG, radiological scans, vital signs measurements), including those that worsen from baseline, considered clinically significant in the medical and scientific judgement of the Investigator (i.e., not related to progression of underlying disease).
- Exacerbation of a chronic or intermittent pre-existing condition including either an increase in frequency and/or intensity of the condition.
- New conditions detected or diagnosed after study treatment administration even though it may have been present before the start of the study.
- Signs, symptoms or the clinical sequelae of a suspected drug-drug interaction.
- Signs, symptoms or the clinical sequelae of a suspected overdose of either study treatment or a concomitant medication. Overdose per se will not be reported as an AE/SAE unless it is an intentional overdose taken with possible suicidal/self-harming intent. Such overdoses should be reported regardless of sequelae.
- "Lack of efficacy" or "failure of expected pharmacological action" per se will not be reported as an AE or SAE. Such instances will be captured in the efficacy assessments. However, the signs, symptoms and/or clinical sequelae resulting from lack of efficacy will be reported as AE or SAE if they fulfil the definition of an AE or SAE.

Events **NOT** Meeting the AE Definition

- Any clinically significant abnormal laboratory findings or other abnormal safety assessments which are associated with the underlying disease, unless judged by the Investigator to be more severe than expected for the subject's condition.
- The disease/disorder being studied or expected progression, signs or symptoms of the disease/disorder being studied, unless more severe than expected for the subject's condition.

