- The causality assessment is one of the criteria used when determining regulatory reporting requirements.

Follow-up of AEs and SAEs

- The Investigator is obligated to perform or arrange for the conduct of supplemental measurements and/or evaluations as medically indicated or as requested by the CRO to elucidate the nature and/or causality of the AE or SAE as fully as possible. This may include additional laboratory tests or investigations, histopathological examinations, or consultation with other health care professionals.
- If a subject dies during participation in the study or during a recognised follow-up period, the Investigator will provide the CRO with a copy of any postmortem findings including histopathology.
- New or updated information will be recorded in the originally completed CRF.
- The Investigator will submit any updated SAE data to the Sponsor within 24 hours of receipt of the information.

Reporting of SAEs

SAE Reporting to the Medical Monitor via an Electronic Data Collection Tool

- The primary mechanism for reporting an SAE to the Medical Monitor will be the electronic data collection tool.
- If the electronic system is unavailable for more than 24 hours, then the study centre will use the paper SAE data collection tool (see next section).
- The study centre will enter the SAE data into the electronic system as soon as it becomes available.
- After the study is completed at a given study centre, the electronic data collection tool will be taken off-line to prevent the entry of new data or changes to existing data.
- If a study centre receives a report of a new SAE from a subject or receives updated data on a previously reported SAE after the electronic data collection tool has been taken off-line, then the study centre can report this information on a paper SAE form (see next section) or to the CRO Safety Team by telephone/fax or email.
- Contacts for SAE reporting can be found in the safety paper forms for the sites.

SAE Reporting to the Medical Monitor via Paper CRF

- The secondary (backup) mechanism for reporting an SAE to the Medical Monitor will be via a paper CRF.
- Facsimile transmission of the SAE paper CRF is the preferred method to transmit this information to the Medical Monitor.
- In rare circumstances and in the absence of facsimile equipment, notification by telephone is acceptable with a copy of the SAE data collection tool sent by overnight mail or courier service.

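### Protocol Section 7.1 stops treatment on INR >1.5 with raised ALT or AST, but no required test supplies INR; separately, the automatic possible Hy's Law SAE rule in Appendix 3 omits AST

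*Protocol*

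**What the plan says.** The liver rules in Protocol Section 7.1 are mandatory once met. One limb stops study drug when ALT or AST is above 3 × ULN and is joined by total bilirubin above 2 × ULN or by "international normalised ratio (INR) >1.5, without any anti-coagulant treatment". The other limbs use enzyme level alone (above 8 ×, or above 5 × for more than 2 weeks), or enzymes above 3 × with listed symptoms or eosinophilia.

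Section 8.2.8 defines the required laboratory tests as those in Appendix 3. Table 13 there lists no INR or other coagulation test, and neither does the laboratory row of the Schedule of Activities. Footnote a of Table 13 sets the possible Hy's Law rule, under which two patterns must be reported as an SAE. The first is ALT at or above 3 × ULN with "bilirubin ≥2 × ULN (>35% direct bilirubin"). The second is ALT at or above 3 × ULN with "international normalised ratio (INR) >1.5, if INR measured, which may indicate severe liver injury". AST appears in neither.

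Some provisions leave room for further testing. Appendix 3 states: "Additional tests may be performed at any time during the study as determined necessary by the Investigator". Appendix 4 obliges the Investigator to carry out or arrange "supplemental measurements and/or evaluations as medically indicated or as requested by the CRO". Section 8.2.8 says that clinically significant results "should be repeated until the values return to normal or baseline" or are no longer judged significant.

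**The concern.** A mandatory stop should not hang on a test that nobody is told to do. The words 'if INR measured' show that the protocol itself expects INR to be absent in some subjects. In such a subject the limb cannot fire, whatever the true INR.

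The second gap is one of reporting. Section 7.1 treats the two enzymes alike and AST is in the required chemistry panel, yet the automatic SAE rule looks at ALT only. A subject can therefore be taken off drug for a possible serious liver signal without the automatic trigger for the 24-hour report in Section 8.3.1.

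The liver is a named area of attention. Section 2.3 lists hepatic toxicity among the events to watch for. Section 4.3 counts raised liver function tests among treatment-related events at 150 mg, while noting that none was clinically significant or serious.

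**Working it through.** No sample size, power or error rate is involved, so the check is a comparison of texts.

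**Step 1: is each input to the Section 7.1 liver rules a required test?**

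| Laboratory input | In Table 13? |
|---|---|
| ALT | Yes, clinical chemistry |
| AST | Yes, clinical chemistry |
| Total bilirubin | Yes, clinical chemistry |
| Eosinophils | Yes, white cell differential |
| INR | No |

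Four of five are required; INR is the exception. Footnote a refers the reader to Section 7.1 for follow-up assessments, but Section 7.1 names only repeat laboratory tests, and repeating Table 13 never yields an INR. SAP Section 15.3 takes its parameters from Appendix 3 and adds none.

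**Step 2: who depends on INR alone?** Removing everyone stopped by another limb leaves a subject who meets all of these conditions:

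- ALT or AST above 3 × ULN, but not above 8 ×, and not above 5 × for more than 2 weeks
- total bilirubin not above 2 × ULN
- none of the listed symptoms and no eosinophilia above 5%
- INR above 1.5, not on an anticoagulant

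**Step 3: which doses could be affected?** Doses fall at Weeks 0, 2, 6 and 10. The laboratory row has entries at Screening and Weeks 0, 2, 6, 10, 12 and 28, but footnote 5 of the Schedule limits Weeks 2, 10 and 28 to CRP and ESR. Chemistry is therefore scheduled at Screening and Weeks 0, 6 and 12.

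- Week 6 is the first on-treatment ALT and AST. It can inform the Week 10 dose, and the Week 6 dose only if results return before injection.
- Week 12 follows the last dose, so nothing remains to withhold.

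Unscheduled tests could add occasions.

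**Step 4: the stopping limb against the SAE rule.**

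| Element | Section 7.1 stop | Footnote a SAE |
|---|---|---|
| Enzyme | ALT or AST >3 × ULN | ALT ≥3 × ULN |
| Bilirubin | Total >2 × ULN | ≥2 × ULN, with >35% direct |
| INR | >1.5, no anticoagulant | >1.5, if measured; anticoagulants not mentioned |

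Two enzymes and two second markers give 2 × 2 = 4 pairs in Section 7.1. Footnote a covers the 2 that involve ALT. With AST >3 × ULN, ALT <3 × ULN, and bilirubin >2 × ULN or INR >1.5 (no anticoagulant), Section 7.1 requires a stop and footnote a is not met, whatever the direct bilirubin share.

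**The case against.** The strongest case against is that the protocol already surrounds both gaps with judgement and oversight. Investigators may order any test and must perform those that are medically indicated. Section 8.2.8 expects unlisted local tests and requires their results in the eCRF when they are clinically significant or change management. An abnormal laboratory value is an AE when "considered clinically significant in the medical and scientific judgement of the Investigator". Section 8.0 adds: "Clinically significant safety concerns should be discussed with the Sponsor immediately upon occurrence or awareness". The Safety Review Team in Section 9.6, which includes an independent Safety Physician, looks at laboratory data and AEs every month. Appendix 4 lets the Investigator judge an AST-only case to be an SAE as an important medical event. A laboratory manual and further Safety Review details exist but are not among the documents.

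Most of this stands, and it is why the point is minor. It does not close the gaps. None of these provisions names INR, none makes an AST-only report automatic, and a monthly review does not replace a 24-hour report. The unseen manual might ask for INR, but Section 8.2.8 says that Appendix 3 defines the required set.

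It is also fair to say that a stopping rule and a reporting rule serve different ends and need not match. A reader might infer that the two contradict each other. They do not: footnote a is narrower on AST and on the direct bilirubin condition, and wider on its ≥ thresholds and on anticoagulated subjects. The case for adding AST is that the protocol measures it and acts on it equally in Section 7.1.

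A reader might also infer uneven practice from up to 10 centres using local laboratories. No text describes how any site handles INR, so that is not supported.

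**Conclusion.** Both parts hold, as a minor patient-safety point about the protocol text.

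- **INR:** one stopping limb has no assured input. The exposure is the residual subject in Step 2. On scheduled chemistry it reaches the Week 10 dose, and the Week 6 dose only under the timing condition in Step 3.
- **AST:** an AST-only case that meets the bilirubin or INR limb stops drug without an automatic SAE report. Only the Investigator's judgement of seriousness would start the 24-hour clock.

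It would be too strong to say that the liver stopping rules do not work, or that AST-only subjects stay on drug. Every limb other than INR runs on required tests or observed symptoms, and the AST-only subject is stopped. Nor can the size be read from counting combinations of raised and normal values: these are logical cases, and the documents give no frequency for them.

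The conclusion assumes that the anticoagulant wording in Section 7.1 qualifies INR only. The dose limit applies to rises that emerge on treatment and are found at scheduled visits. No estimand, sample size or analysis is affected.

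**What to change.** 1. **Footnote a of Table 13:** change 'ALT' to 'ALT or AST' in both the bilirubin and the INR limb. This stands on its own and needs no new test.
2. **Section 7.1:** require a local INR whenever ALT or AST exceeds 3 × ULN, with the result reviewed before the next dose.
3. **Table 13:** list INR as a reflex test at the same trigger, then delete 'if INR measured' from footnote a.

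Leave the >35% direct bilirubin condition as it is; direct bilirubin is already in Table 13. Stopped subjects who fail that condition and do not meet the INR limb will still have no automatic report. Do not carry the anticoagulant exemption into footnote a, because that would remove SAE reports that are mandatory now.

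The cost is wording changes in three places, an occasional local blood test and possibly a few more SAE reports.

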7.2 Subject Discontinuation/Withdrawal from the Study

A subject may withdraw from the study at any time at his/her own request or may be withdrawn at any time at the discretion of the Investigator for safety, behavioural, compliance or administrative reasons.

If the subject withdraws consent for disclosure of future information, the Sponsor may retain and continue to use any data collected before such a withdrawal of consent.

If a subject withdraws from the study, he/she may request destruction of any samples taken and not tested, and the Investigator must document this in the study centre study records.

See SoA for data to be collected at the time of study discontinuation and follow-up and for any further evaluations that need to be completed.

